## **16. ETHICS**

### **16.1. Ethics Review**

The final study protocol and the final version of the ICF must be approved or given a favorable opinion in writing by an ethics committee, as appropriate. The investigator must submit written approval from the ethics committee to BioCryst before he or she can enroll any subject into the study.

The ethics committee will be informed of any amendment to the protocol in accordance with local requirements. In addition, the ethics committee must approve any advertising used to recruit subjects for the study. The protocol must be re-approved by the ethics committee upon receipt of amendments and annually, as local regulations require.

The ethics committee will be provided with reports of any reportable serious adverse drug reactions from any other study conducted with the investigational product, in accordance with local regulations. BioCryst will provide this information to the investigator.

Progress reports and notifications of serious adverse drug reactions will be provided to the ethics committee according to local regulations and guidelines.

### **16.2. Ethical Conduct of the Study**

The study will be performed in accordance with ethical principles that have their origin in the Declaration of Helsinki and are consistent with ICH GCP, applicable regulatory requirements, and BioCryst's policies.

### **16.3. Written Informed Consent**

In accordance with applicable national or local law, and current institutional practice, written informed consent to participate in the study will be obtained from each subject prior to conducting any study-related assessments/procedures.

A signed ICF must be obtained from each subject prior to performing any study-related procedures. Each subject should be given both oral and written information describing the nature, purpose, and duration of the study. Subjects will be informed that they are free not to participate in the study and that they may withdraw consent to participate at any time. They will be told that refusal to participate in the study will not prejudice future treatment. They will also be told that their records may be examined by competent authorities and authorized persons, but that personal information will be treated as strictly confidential and will not be publicly available. The informed consent process should take place under conditions where the subject has adequate time to consider the risks and benefits associated with participation in the study. Subjects must be given the opportunity to ask questions. Subjects will not be screened or treated until the subject has signed an approved ICF written in a language in which the subject is fluent.

The ICF that is used must be approved both by BioCryst and by the governing ethics committee. The ICF should be in accordance with the current revision of the Declaration of Helsinki, current ICH and GCP guidelines, and BioCryst policies.

The subject should receive a signed and dated copy of the ICF. The original signed ICF should be retained in the study files.

The investigator shall maintain a log of all subjects for whom consent was signed and indicate if the subject was enrolled into the study or reason for non-enrollment.

## **17. DATA HANDLING AND RECORDKEEPING**

### **17.1. Inspection of Records**

BioCryst or designee will be allowed to conduct site visits to the investigation facilities for the purpose of monitoring any aspect of the study. The investigator agrees to allow the monitor to inspect the drug storage area, study drug stocks, drug accountability records, subject charts and study source documents, and other records relative to study conduct.

### **17.2. Retention of Records**

The investigator will maintain adequate records for the study, including the identity of all participating subjects (sufficient information to link records, eCRFs, and medical/hospital records), all original signed ICFs, all original signed assents (if applicable), all eCRFs, drug dispensing and disposition records, safety reports, information regarding participants who discontinued, and other pertinent data.

All essential documents should be retained by the investigator according to local regulations or as specified in the Clinical Study Agreement, whichever is longer. It is the responsibility of BioCryst to inform the investigator/institution as to when these documents no longer need to be retained. It is the investigator's responsibility to notify BioCryst if they relocate or retire so that document storage can be addressed. The investigator must obtain BioCryst's written permission before disposing of any records and must notify BioCryst before transferring any records to another facility.

All correspondence related to records retention, destruction, or transfer of study documents, should be sent directly to BioCryst study personnel, copying the email [[contact]](mailto:[contact]).

### **17.3. Confidentiality of Information and Data**

BioCryst affirms the subject's right to protection against invasion of privacy and secure maintenance of the confidential nature of his/her personal data. Only a subject identification number and subject identifiers permitted by local regulation will identify subject data retrieved by BioCryst. However, in compliance with federal regulations, BioCryst requires the investigator to permit BioCryst's representatives and, when necessary, representatives of the FDA or other regulatory authorities to review and/or copy any medical records relevant to the study, maintaining pseudo-anonymity.

All parties will abide by all applicable laws and regulations regarding subject privacy and confidentiality, including the Health Insurance Portability and Accountability Act (HIPAA), where this rule is applicable, and the requirements of the General Data Protection Regulation (GDPR) in the EU, where applicable. A valid authorization and consent must meet the specifications of the applicable laws and regulations relating to such personal data and health information. It is the responsibility of the investigator and institution to obtain such

waiver/authorization in writing from the appropriate individual. HIPAA authorizations are required for US sites only.

## **18. PUBLICATION POLICY**

All data generated from this study are the property of BioCryst and shall be held in strict confidence along with all information furnished by BioCryst. Except as provided through written agreement between BioCryst, independent analysis and/or publication of these data by the investigator or any member of his/her staff is not permitted without prior written consent of BioCryst. Such consent will not be withheld unreasonably. BioCryst is in agreement with the principle of full disclosure of clinical study results.

## Technical Summary Report (TSR)

Name of Sponsor/Company BioCryst Pharmaceuticals, Inc.	Individual Study Table Referring to Part of the Dossier: Volume:	(For National Authority Use Only):		
Name of Finished Product: BCX9930	Page:			
Name of Active Ingredient: 2-(2-((7-(2-(aminomethyl)-3-fluoropyridin-4-yl)benzofuran-5-yl)methoxy)phenyl)acetic acid				
Title of Study: An Open-label Study to Evaluate the Long-term Safety of BCX9930 Monotherapy in Subjects with Paroxysmal Nocturnal Hemoglobinuria Who Previously Received BCX9930 in a BioCryst-sponsored Study (BioCryst Protocol BCX9930-205)				
Investigators: Study Centers: This study will be conducted at study centers in multiple countries/regions				
Studied period (years): Approximately 2 years	Phase of development: Phase 2b			
Introduction BioCryst stopped development of BCX9930 in December of 2022 based on changes in the competitive environment. This statistical analysis plan contains a detailed description of the statistical methods to support the abbreviated clinical study report (aCSR) for this study.				
Objectives: 
 
To provide continued access to BCX9930 for subjects with PNH who have benefited from treatment with BCX9930 in another BioCryst-sponsored study and who, in the opinion of the investigator, would benefit from continued treatment with BCX9930, and who do not have access to other effective treatment options
 
To monitor the safety of BCX9930 in subjects continuing to receive BCX9930 for the treatment of PNH
 
				
Endpoints: 
 
Subject incidence of graded treatment-emergent adverse events (TEAEs), laboratory abnormalities, changes to vital signs, and physical examination findings
 
				
Study Design: This study is designed to provide continued access to BCX9930 for subjects currently receiving treatment with BCX9930 in another BioCryst-sponsored clinical study for PNH (i.e., Studies 201, 202, or 203, hereafter referred to as the “prior study”) who, in the opinion of the				

investigator, have both benefited from treatment with BCX9930 and would benefit from continued treatment with BCX9930, who wish to continue treatment, and who do not have access to other effective treatment options.

Subjects will be eligible to receive study drug (BCX9930) under this version of the protocol for up to 96 weeks for as long as the investigator believes it is in the subject's best interest to continue treatment, or until the subject has access to another therapy for PNH, whichever comes first. Treatment with BCX9930 will be discontinued for subjects who are deriving no meaningful clinical benefit, or who experience an unacceptable drug-related AE or are otherwise intolerant of study drug.

An independent BCX9930 program-wide DMC will provide oversight of the safety of subjects receiving BCX9930 in this study.

*Methodology:*

Subjects who meet all of the inclusion and none of the exclusion criteria can be enrolled into Study 205. The last on-treatment visit completed for the prior study will also serve as the baseline visit for Study 205. If subjects have completed at least 24 weeks of BCX9930 treatment in the prior study, study visits will occur every 8 weeks to Week 48, then every 12 weeks until Week 96. Subjects who have not completed 24 weeks of treatment with BCX9930 prior to enrolling in Study 205 must return to the clinic every 4 weeks until they have completed 24 weeks of cumulative treatment with BCX9930. Subjects who discontinue treatment with BCX9930 for any reason (complete study visits or discontinue early), will be asked to complete an end-of-study or early termination visit, as applicable, approximately 3 weeks ( $\pm$  3 days) after the last dose of BCX9930.

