## 2. SYNOPSIS

Name of Sponsor/Company: BioCryst Pharmaceuticals, Inc.
Name of Investigational Product: BCX9930
Name of Active Ingredient: 2-(2-((7-(2-(aminomethyl)-3-fluoropyridin-4-yl)benzofuran-5-yl)methoxy)phenyl)acetic acid
Title of Study: An Open-label Study to Evaluate the Long-term Safety of BCX9930 Monotherapy in Subjects with Paroxysmal Nocturnal Hemoglobinuria Who Previously Received BCX9930 in a BioCryst-sponsored Study
BioCryst Protocol No.: BCX9930-205
Regulatory Agency Identifier Number(s): EudraCT No. 2021-006776-17 EU CT Number: 2023-507315-35 UTN Number: U1111-1295-6848
Study Centers: This study will be conducted at study centers in multiple countries/regions
Lead or Coordinating Investigator: PPD  PPD 
Phase of development: 2b
Objectives 

• To provide continued access to BCX9930 for subjects with paroxysmal nocturnal hemoglobinuria (PNH) who have benefited from treatment with BCX9930 in another BioCryst-sponsored study and who, in the opinion of the investigator, would benefit from continued treatment with BCX9930, and who do not have access to other effective treatment options

• To monitor the safety of BCX9930 in subjects continuing to receive BCX9930 for the treatment of PNH

Endpoints 

• Subject incidence of graded treatment-emergent adverse events (TEAEs), laboratory abnormalities, changes to vital signs, and physical examination findings

Study Design: This study is designed to provide continued access to treatment with BCX9930 for subjects currently receiving treatment with BCX9930 in another BioCryst-sponsored clinical study for PNH (ie, Studies BCX9930-201, -202, and -203, hereafter referred to as the “prior study”) who, in the opinion of the

investigator, have both benefited from treatment with BCX9930 and would benefit from continued treatment with BCX9930, who wish to continue treatment, and who do not have access to other effective treatment options.

*Methodology:*

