### 6.2. Endpoints

The endpoints of this study are:

- Subject incidence of graded TEAEs, laboratory abnormalities, changes to vital signs, and physical examination findings

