b Visits may be performed within a window of  $\pm$  6 days. Subjects who have not completed 24 weeks of treatment with BCX9930 prior to entering this study must return to the clinic every 4 weeks until they have completed 24 weeks of cumulative treatment. Subjects with **CCI** [REDACTED] will be required to complete additional assessments **CCI** [REDACTED] at the investigational site, or at a remote laboratory more convenient for the subject as indicated in Section 10.3.1 and Section 12.5.2. Additional visits may be required for subjects who experience hemolysis on study or following the permanent discontinuation of BCX9930, or who require unscheduled visits for additional or repeat evaluations. Subjects do not need to withhold any BCX9930 doses on clinic days or take a dose in the clinic, unless the clinic visit falls during the subject's normal time of dosing.

c Subjects who discontinue dosing with BCX9930 for any reason (complete study visits or discontinue early), will be asked to complete an EOS or ET visit, as applicable, approximately 3 weeks ( $\pm$  3 days) after last dose of BCX9930.

d Medical and medication history will be obtained from the prior study.

e For those who entered the prior study with positive serology for HIV or active infection with HBV or HCV, the appropriate testing for viral load should be repeated approximately yearly from the date of first viral load assessment. If positive, contact the medical monitor to discuss the best option for the subject.

f Symptom-directed physical examinations will be performed at all regularly scheduled visits.

g To include blood pressure, pulse rate, and temperature. Prior to obtaining blood pressure and pulse rate, subjects should rest quietly for a brief period.

h Cholesterol and triglycerides will be measured every 6 months (ie, Weeks 24, 48, 72, and 96).

i PNH RBC and WBC clone size included.

j Urine microscopy will be performed at the central laboratory as reflex testing in the event of an abnormal urinalysis.

k For women of childbearing potential, a urine pregnancy test will be assessed at baseline, at onsite visits during the treatment period, and at the EOS/ET visit. Women of childbearing potential will be provided with urine pregnancy test kits for home testing once a month.

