### 13.3.4. Analysis of Safety Variables

Safety endpoints will be summarized and will include, at a minimum, the proportion of subjects 1) with TEAEs; 2) who discontinue due to a TEAE; 3) with treatment-emergent SAE; 4) with a Grade 3 or 4 TEAE; and 5) with Grade 3 or 4 laboratory abnormalities.

AEs will be mapped to a Medical Dictionary for Regulatory Activities (MedDRA, Version 24.0) preferred term and system organ classification. The occurrence of TEAEs will be summarized using MedDRA preferred terms, system organ classifications, and severity. In addition to severity, AEs and SAEs will also be summarized based on investigator assessment of relationship to study drug.

For all analyses of change from baseline, the baseline is the baseline value for the current study.

Descriptive statistics for vital signs, weight, and clinical laboratory results will be presented by study visit. Laboratory abnormalities will be graded according to CTCAE scales (Version 5.0, 27 November 2017). The number and percentage of subjects experiencing treatment-emergent graded laboratory toxicities will be summarized. Laboratory toxicity shifts from baseline to the worst post-baseline value as well as to the last visit will be summarized.

The number and percentage of subjects having elevations in ALT, AST, or bilirubin abnormalities in relation to fold above ULN will be summarized according to the US FDA's Premarketing Clinical Evaluation on Drug-Induced Liver Injury Guidance for Industry ([FDA 2009](#)).

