### 2.2. Endpoints

The endpoints of this study are:

- Subject incidence of graded treatment-emergent adverse events (TEAEs) and laboratory abnormalities.

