## **8. SAFETY AND TOLERABILITY**

All study safety data to support the aCSR will be presented in data listings.

AEs will be assessed and recorded from the time of signing of the informed consent through the appropriate follow-up period. AEs will be mapped to MedDRA version 24.0 preferred term (PT) and system organ class (SOC). Relationship to study treatment will be assessed as not related, unlikely related, possibly related, probably related, or definitely related. AEs will be graded according to the CTCAE scales (Version 5.0, 27 November 2017). AEs not covered by CTCAE criteria will be assessed for severity as mild, moderate, severe, or life-threatening, corresponding to toxicity Grades 1 through 4.

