## 9. CHANGES FROM PROTOCOL-SPECIFIED ANALYSES

Due to the discontinuation of the BCX9930 drug development by the sponsor, only variables relevant to the aCSR will be summarized and listed.

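### SAP Section 2.2 omits vital-sign changes and physical examination findings, two of the four stated endpoint parts; no planned table or listing reports them, and Section 9 does not name them as removed

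*SAP*

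**What the plan says.** Protocol Section 6.2 defines the endpoint as "Subject incidence of graded TEAEs, laboratory abnormalities, changes to vital signs, and physical examination findings". The protocol synopsis has the same four parts, ending with "laboratory abnormalities, changes to vital signs, and physical examination findings". The SAP's Technical Summary Report repeats them, including "changes to vital signs, and physical examination findings". SAP Section 2.2, the section that governs the analysis, reads "Subject incidence of graded treatment-emergent adverse events (TEAEs) and laboratory abnormalities" and stops there.

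On collection, Table 2 of the protocol marks vital signs and a physical examination at baseline, at the treatment visits and at the end-of-study or early-termination visit. A footnote adds: "Symptom-directed physical examinations will be performed at all regularly scheduled visits".

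On analysis, Protocol Section 13.3.4 says: "Descriptive statistics for vital signs, weight, and clinical laboratory results will be presented by study visit". It specifies no separate summary of physical examination findings. SAP Section 8 opens with "All study safety data to support the aCSR will be presented in data listings" and then describes adverse-event summaries only.

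On departures from the protocol, SAP Section 9 explains that, because development was discontinued, "only variables relevant to the aCSR will be summarized and listed". It does not mention vital signs or physical examination.

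**The concern.** The SAP gives two different endpoint statements, and the shorter one also departs from the protocol. A programmer who follows Section 2.2 and the display list will produce nothing on two endpoint parts. A reader of the Technical Summary will expect to find them.

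The study has two objectives, continued access and safety monitoring, so safety is the only one that calls for analysis. The protocol's benefit-risk section counts vital signs and physical examination findings among the parameters whose regular monitoring is meant to support continued dosing, and the synopsis names both as criteria for evaluation. Leaving them out may be a defensible choice for an abbreviated report. It should then be visible as a choice, and the section reserved for changes from the protocol does not show it.

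**Working it through.** No formula applies. The documents give no sample-size calculation and no hypothesis, so the check compares the endpoint statements and counts the planned displays.

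**1. Endpoint statements**

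| Source | Graded TEAEs | Laboratory abnormalities | Vital-sign changes | Physical findings |
|---|---|---|---|---|
| Protocol synopsis | yes | yes | yes | yes |
| Protocol 6.2 | yes | yes | yes | yes |
| SAP Technical Summary | yes | yes | yes | yes |
| SAP 2.2 | yes | yes | no | no |

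Three statements have four parts and one has two: 4 − 2 = 2 parts missing.

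**2. Planned displays**

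- SAP 9.1.1 tables: 4 on study population + 2 under efficacy (hemoglobin, LDH) + 6 on adverse events = 12. Tables on vital signs or physical findings: 0.
- SAP 9.1.2 listings: 13, of which four concern adverse events and one (16.2.8) concerns Grade 3 or 4 laboratory abnormalities. Listings of vital signs or physical findings: 0.
- Total: 12 + 13 = 25 displays, 0 for the two missing parts.

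**3. Could another provision bring them in?** SAP 9.1 lets listings be added without a revision when they support the tables. No planned table concerns these data, so that allowance does not reach them.

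**4. Does the stop of development explain the cut?** Development stopped in December 2022. Protocol v4.0 is dated 27 July 2023. It states in Section 11.4 that specific effectiveness assessments are no longer required, and it still keeps the four-part endpoint. The two parts thus remained endpoints after the stop. The SAP meanwhile tabulates hemoglobin and LDH as efficacy, although Protocol 6.2 contains no efficacy endpoint. So the selection for the aCSR does not follow the endpoint list, and the SAP does not say what it follows.

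**5. What would adverse-event reporting catch?** Under Protocol 12.1.1, clinically relevant abnormal results and new or worsening signs are adverse events. Results that are incidental, or that lead to no further treatment, visit or monitoring, are not. The first kind would reach the adverse-event tables and Listing 16.2.7.1. The second kind, and all by-visit values, would reach no planned display.

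**6. Vital signs and physical findings differ.** For vital signs, both the endpoint and the analysis in Protocol 13.3.4 are unserved. For physical findings the protocol planned no summary, so that gap rests on the endpoint statement alone.

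**The case against.** The best defence is that the cut is deliberate and disclosed. The SAP says at the outset that it supports an abbreviated report, Section 9 says outputs were reduced for that reason, and Section 2.2 states a reduced endpoint consistent with the displays. On this view the Technical Summary is simply protocol text that was carried over and not updated. That may well be what happened. It does not remove the point: the SAP still contradicts itself, and Section 9 never says that stated endpoint parts were dropped.

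Four further objections limit how far the point can be pushed.

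- A reader might take SAP Section 8 as promising that every safety variable will be listed, so that the missing listing breaks the SAP's own rule. The sentence covers only data that support the aCSR, which agrees with Section 9. It makes no such promise.
- A reader might infer that the study could say nothing at all about blood pressure, pulse or temperature. That goes too far. Fever or hypertension of clinical relevance should appear as adverse events, and renal events have their own table and listing.
- Physical examinations are symptom-directed and look for new or worsening signs or symptoms, which overlap largely with adverse events. Less is lost there than for vital signs.
- The data monitoring committee may see these data. Its outputs are set in a charter that is not among the documents, so the claim must stay with the planned aCSR displays.

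All four stand as limits. None of them supplies the missing by-visit values.

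**Conclusion.** The point holds as a reporting gap that should be corrected. Two of the four endpoint parts are absent from SAP 2.2 and from all 25 planned displays. For one of them, vital signs, an analysis written into the protocol is also missing. The aCSR as planned could make no systematic statement on either part beyond what adverse-event reporting happens to capture.

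A reader might want to size the loss as the 12 scheduled occasions in Table 2 (baseline, 10 treatment visits, end-of-study or early-termination visit) times the planned 30 subjects. The documents do not support that product as a maximum or as an expectation. A subject who enters with the minimum 12 weeks of prior treatment needs 4-weekly visits for 12 more weeks, which adds Weeks 4 and 12 and makes 12 + 2 = 14. In the other direction, 30 is an upper estimate and subjects leave once they have access to another therapy. A count of unreported records would not show in any case that a conclusion changes: the study is single-arm and descriptive, with no hypotheses.

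The verdict assumes that the lists in SAP 9.1 are the complete planned output and that no separate document adds vital-sign displays to the aCSR.

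**What to change.** Preferred:

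1. Restore the four-part endpoint in SAP 2.2 so that it agrees with Protocol 6.2 and the SAP's Technical Summary.
2. Add to SAP 8 and 9.1.1 the by-visit vital-signs table that Protocol 13.3.4 specifies, with observed values and change from the Study 205 baseline for blood pressure, pulse rate and temperature. Weight is named in the same protocol sentence, but Table 2 schedules it at baseline only, so no by-visit weight display is asked for.
3. Add to 9.1.2 one listing of vital signs and one of physical examination findings. A summary table of physical findings is not needed, since the protocol planned none.

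The cost is programming and checking one table and two listings from data already collected. Before programming, confirm that baseline values from the prior study's last on-treatment visit are in the Study 205 database; SAP 5.5.1 gives a fallback if they are not.

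If the omission is deliberate, align the Technical Summary with Section 2.2 and state in Section 9 that vital-sign changes and physical examination findings were removed from the endpoint and its reporting, and why. This costs only text. The SAP carries an approval dated 07-Feb-2025. If it can no longer be revised before database lock, record the same statement in the study report as a deviation, as SAP Section 1 provides for departures from the approved plan.
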